17.3 Sample size and recruitment

17.3.1 Sample size calculation

As stated above, the primary outcome measure will be the change in total health status score of the K-BILD questionnaire that we have planned to collect every two weeks at each visit from V1 to V4 (14). Patients will be randomized to ambulatory oxygen or not, crossing over to the alternative arm after two weeks. The repeatability of the K-BILD questionnaire at

two weeks in patients with stable ILD is high, with an intra-class coefficient of 0.94 for the total health status score. This study is powered to detect a change of 8 units in the K-BILD total score, the minimally clinically important difference (SD: 20), recently estimated by using a range of distribution methods and anchoring K-BILD change against change in FVC and other established respiratory questionnaires (26).

We calculated that a sample size of 80 patients would allow 90% power at 5% significance to detect a difference of at least 8 points between the two crossover trial arms, allowing for a 15% drop out rate. This degree of power will also allow us to perform some exploratory subgroup analyses. For example, sub analysis of IPF patients only will be possible with adequate power. If we consider that IPF patients form 70% of the sample, this number of IPF patients (56) would still provide a power of 84% to detect a difference of 8 in the K-BILD health status score.

The software used for power calculations was "PS Power and Sample Size calculator version 3.0 by William Dupont and Walton Plummer 2009".

17.3.2 *Planned recruitment rate*

Recruitment of 80 patients with fibrotic ILD will occur over an 18 month period. Based on review of current practice, we are confident of recruiting 50 patients at RBH, and 15 each at KCH and Aintree over this period. IPF patients currently in the Profile study ("prospective observation of fibrosis in the lung clinical endpoints NCT01110694; > 100 currently enrolled) can enrol in this study.

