11.3 Definition of the End of Trial

The end of the trial will coincide with the Last Patient Last Visit (LPLV).

12 Discontinuation/withdrawal of participants and stopping rules

As we do not expect there to be any toxicity from the use of ambulatory oxygen, subjects will be withdrawn from the trial only if they wish to do so. We will ask any patient who wishes to withdraw from the study, if they are willing, to fill in the relevant questionnaires at the end of the two and four week period, if needed *via* telephone, so as to be able to compare change in health status and other questionnaire related outcomes compared to baseline, against subjects completing the trial.

As our power calculations have allowed for subject withdrawals and incomplete data in a subset of patients, we do not expect the need to replace subjects, unless < 50 complete the study.

We do not envisage prematurely stopping the trial, again in view of the lack of toxicity of ambulatory oxygen in the patients selected for this trial.

13 IMPs and non-IMPs used in the trial

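### The protocol gives the main power after 15% dropout but the IPF subgroup power before it (84% stated, about 77% on the same basis), and section 12 cites the power calculation for losses far beyond those it allowed

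*Protocol*

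**What the plan says.** Section 17.3.1 plans "to detect a difference of at least 8 points between the two crossover trial arms" on the K-BILD total score. It calls 8 points "the minimally clinically important difference (SD: 20"). It states that "a sample size of 80 patients would allow 90% power at 5% significance", and it describes this figure as "allowing for a 15% drop out rate".

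The same paragraph turns to exploratory subgroup analyses and gives IPF as its example: "If we consider that IPF patients form 70% of the sample", then "this number of IPF patients (56) would still provide a power of 84" per cent for the same 8-point difference. It describes this power as adequate. Section 17.4.2 lists IPF among the predefined subgroups to be analysed separately.

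Section 12 deals with replacement. The rule is that "we do not expect the need to replace subjects, unless < 50 complete the study". The reason offered for that rule is the sample size calculation, in these words: "As our power calculations have allowed for subject withdrawals and incomplete data in a subset of patients".

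**The concern.** The two power figures in section 17.3.1 stand side by side and invite comparison, 90% for the whole trial and 84% for IPF. If one is computed after dropout and the other before it, the comparison flatters the subgroup, and the claim of adequate power rests on a number the protocol's own assumptions do not give.

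Section 12 uses the power calculation as its reason for not replacing patients, but then sets a floor that does not come from that calculation. A reader would take it that losses down to 50 completers have been allowed for. What is at stake is how accurately the protocol describes its own power, for an exploratory subgroup and for the primary endpoint under heavy attrition. The design, the primary analysis and the type I error are not affected.

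**Working it through.** **Inputs.** All come from section 17.3.1 unless noted: difference 8; SD 20; significance 5%; target power 90%; 80 enrolled; dropout 15%; IPF share 70%. The paired t-test is named in section 17.4.2 and the floor of 50 completers in section 12.

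**Two readings the protocol leaves open.** It does not say which SD the 20 is, or whether the test is one- or two-sided. I take the SD of within-patient differences and a two-sided test, because this reproduces the stated figures.

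**Formula.** For n pairs, the noncentrality is δ = (8/20) × √n = 0.4√n, with n − 1 degrees of freedom. Power is the probability that a noncentral t variable with these parameters falls outside ± the 97.5% point of the central t.

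| Paired patients n | δ = 0.4√n | Power | What n represents |
|---|---|---|---|
| 80 | 3.58 | 94.2% | all enrolled, no loss |
| 68 | 3.30 | 90.2% | 80 × 0.85 |
| 67 | 3.27 | 89.7% | one fewer |
| 56 | 2.99 | 83.7% | 0.70 × 80, no loss |
| 50 | 2.83 | 79.2% | floor in section 12 |
| 48 | 2.77 | 77.5% | 56 × 0.85 = 47.6, rounded up |
| 47 | 2.74 | 76.6% | 47.6 rounded down |

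**Step 1: main figure.** The smallest n with at least 90% power is 68, and 68 / 0.85 = 80. The stated 80 is reproduced exactly, with the 15% built in.

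**Step 2: IPF figure.** 0.70 × 80 = 56, and n = 56 gives 83.7%, which rounds to the stated 84%. So the 84% assumes that all 56 enrolled IPF patients are analysed.

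**Step 3: same basis for both.** 56 × 0.85 = 47.6, giving 76.6% to 77.5%, about 77%. Taking 70% of the 68 completers gives the same 47.6. The like-for-like comparison is 90% against about 77%.

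**Step 4: replacement floor.** The calculation allows 80 − 68 = 12 losses (15%). The floor tolerates 80 − 50 = 30 losses, and 30/80 = 37.5%, which is 2.5 times as many. With 50 pairs power is 79.2%, a type II error of about 21% against about 10% at 68.

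**Sensitivity to the reading.** Other readings do not give 84% for IPF:
- A one-sided 5% test at n = 56 gives 90.5%.
- A two-sample formula gives 32% (28 per group) to 56% (56 per group).
- An SD of differences derived from the intra-class correlation of 0.94, 20 × √(2 × 0.06) = 6.9, gives over 99.9%.

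Using the normal approximation in place of the t distribution gives 78.3% to 79.1% at 47 to 48 pairs and 80.7% at 50, so the conclusions stay the same.

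**The case against.** - **The IPF sentence is true as worded.** For 56 analysed patients 84% is right, and the analysis is offered as an exploratory example under an assumed 70% share. This stands, and it lowers the weight of the point. But the sentence directly before it allows for 15% dropout, and this one drops the allowance without saying so.
- **No threshold for adequate power is defined.** This stands too. Whether 77% is adequate is a judgement, so the claim should be qualified by the right figure; it is not refuted.
- **Completers are not the same as analysed patients.** Section 12 asks willing patients who withdraw to fill in the questionnaires at two and four weeks, by telephone if needed, and the primary analysis is by intention to treat. This stands: 79% is the power at 50 paired observations, and 50 completers could yield more than 50 pairs.
- **A replacement floor need not equal the planned number of completers.** This also stands. Fifty could have been chosen as a point of roughly 80% power, although the protocol does not say so. What remains is that section 12 gives the power calculation as its reason, and that calculation covers 12 losses, not 30.

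A reader might infer that the protocol claims 90% power at 50 completers, or would report 90% whatever the attrition. Neither is supported. Section 12 gives no power for 50, and section 17.3.1 ties its 90% to 15% dropout.

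**Conclusion.** The point holds at minor to moderate severity. On the plan's own inputs the IPF power is about 77% once the 15% loss is applied, some 7 percentage points below the stated 84%. Section 12 cites the power calculation as cover for losses that it did not allow for. Power falls from about 90% at 68 pairs to about 79% at 50, and that lower figure applies only if no more than 50 patients supply paired K-BILD data.

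The figures assume that SD 20 is the SD of within-patient differences, that the test is a two-sided 5% paired t-test, and that IPF patients drop out at the overall 15% rate.

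A reader might also conclude that the dropout allowance is missing altogether, or that the trial is too small. The document does not support that: the calculation that sizes the trial carries the 15% through correctly, and 80 is right.

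**What to change.** **Section 17.3.1.** State that 56 is the number of IPF patients enrolled, that about 48 are expected to be evaluable after 15% dropout, and that power is then about 77%. Qualify the claim of adequate power to match. If the 84% is kept as well, label it as the power with no dropout.

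**Section 12.** Keep the floor of 50 if it is wanted, but state that power at 50 paired observations is about 79% and that 90% requires 68. Remove the implication that the power calculation covers losses down to 50. Raising the floor to 68 is not needed as a correction; it could require replacement recruitment from the 13th loss onwards.

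**Also in section 17.3.1.** Say that SD 20 is the SD of within-patient differences and that the test is two-sided, if that is what was used.

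**Cost.** A few sentences of wording and a less favourable stated power for the subgroup. No extra patients are needed, and the design and the analysis do not change.

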17.4 Statistical analysis plan

17.4.1 *Summary of baseline data and flow of patients*

As the design of the study is a crossover trial, there will be no baseline comparison. Summary statistics will be presented to reflect the type of data, with categorical presented as %, and numerical data as mean \pm SD or median with interquartile range, as appropriate. Some numeric variable will be presented both as continuous and as categorical based on known relevant cut-offs or thresholds.

A consort-statement diagram will be presented.

17.4.2 *Primary endpoint analysis*

The primary endpoint will be the change in K-BILD health status score. The mean change vs baseline in the K-BILD health status score on and off ambulatory oxygen will be compared by using either a paired t-test or Wilcoxon signed rank test, as appropriate to the distribution of the data. To allow assessment of the effect of baseline values on treatment and any other potential confounders, regression with robust variances or linear mixed models will be used. STATA software will be used for statistical analysis.

Predefined subgroup analysis will include an assessment of whether patients with elevated BNP and/or evidence of pulmonary hypertension on echo re more likely to benefit from ambulatory oxygen. Also patients with IPF which we expect to be the largest subgroup will

be analysed separately. IPF patients tend to experience the most severe desaturation on exertion and may therefore respond differently to supplemental oxygen than other fibrotic ILDs.

We expect missing data to be low. All data will be checked for validity and where data is questionable the appropriate investigator will query and resolve the inconsistency. For outlier values believed to be correct, a sensitivity analysis will be performed with and without such values. Subgroup analysis will follow the same analysis used for the primary outcome.

Our primary analysis will be based on intention to treat.

Qualitative methods: For the qualitative interview analysis, interviews will be transcribed verbatim. Interview transcripts will be analysed thematically using a framework approach (21). Through the five steps of (1) familiarisation, (2) identifying thematic framework, (3) indexing, (4) charting, and (5) mapping and interpretation, framework provides a systematic approach to analysis useful for applied qualitative research and enhances visibility of analysis for policy-makers and practitioners. It is the method of choice for this study as it enables results to be produced relatively quickly to inform policy or practice, as well being useful for studies where data collection is more structured, and where analysis needs to be viewed/assessed by others in the team (20). Further, it is particularly useful for linking qualitative to quantitative data which would facilitate a mixed methods analysis of the broader dataset thus providing comprehensiveness and greater knowledge yield (21;27) making best use of the data collected. Atlas/ti computer software (<http://www.atlasti.com>) will be used to manage and index the data prior to charting, mapping and interpretation.

17.4.3 Secondary endpoint analysis

For all continuous variables we will use a paired t-test or a Wilcoxon signed rank test, as appropriate. For categorical variables, a Wilcoxon signed rank test or paired ChiSquare will be used as appropriate. To allow assessment of the effect of baseline values on treatment and any other potential confounders, regression with robust variances or linear mixed models will be used.

17.5 Randomisation

Simple block method randomization will be performed to determine the order of treatment. As the study is un-blinded, varying block sizes will not be required.

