6.1 Overall design

The planned non-commercial study is a randomised, controlled crossover trial of ambulatory oxygen against no ambulatory oxygen over a four week period (two weeks on ambulatory oxygen and two weeks on air), to evaluate the effects of ambulatory oxygen on health status in patients with ILD. A short crossover study in this context has many advantages, since ambulatory oxygen has immediate effect, with no wash-out period needed after use.

At the start of the trial, the effects of ambulatory oxygen on 6 Minute Walk Test (6MWT) performances will be evaluated on oxygen and on air-filled canisters, with the patient blind to the contents of the canister, to assess whether oxygen-induced improvements in 6MWT parameters can predict its effectiveness in day to day life. The 6MWT is a well-established and highly reproducible test validated in ILD patients (8; 9), with significant prognostic implications (10).

The study design does not include a placebo arm because:

- a) The intervention is a combination of possible benefits from oxygen and the disadvantage of canister weight. These cannot be separated. Placebo control is impossible because there is no means of providing placebo weight. Attempts to control solely for oxygen use without taking canister weight into account are clinically meaningless. In a recent COPD study, cylinder weight was reported as a barrier to use by 93% of study participants (11).
- b) A positive result against an air-filled canister arm would be clinically uninterpretable. This is a study design in which the 'placebo' would be actively harmful to study participants. Carriage of an air-filled cylinder would be expected to lead to earlier desaturation and reduced exercise tolerance. Such a design would not inform the real life comparison between oxygen plus cylinder and no intervention.

- c) All this aside, blinding is legally impossible (UK health and safety regulations **require** that oxygen cylinders for home use must be clearly labelled).

It should also be stressed that objective measures of change are evaluated as secondary end-points: we expect to explore correlations between these variables and the primary end-point to exclude the possibility that an observed treatment benefit on the primary end-point might be confounded by a placebo effect.

6.1.1 Target population and screening:

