9.2 Randomisation procedure

All study patients will be randomized twice during the baseline study visit:

1. Randomisation as to the order in which subjects will perform the 6MWT on oxygen *versus* air. The patients will be blind to the content of the canister.
2. Randomisation as to the order in which subjects will have the portable home oxygen *versus* no oxygen during the first two weeks of treatment.

The Trust Statistician, [name], will provide a master randomization list that will form basis of the study randomization *via* an InForm database set up by Imperial College Clinical Trials Unit (ICTU).

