10.4 Baseline assessments and Randomization (Visit 2 in Week 0)

Following the run-in period at the baseline visit (visit 2), stability of respiratory symptoms will be assessed according to routine clinical care. Only patients with stable symptoms (no chest infections and no changes in medications) during four weeks before including the run in period will be assigned in random order to two weeks on ambulatory oxygen or not treatment for two weeks.

Patients will be invited to perform two 6MWTs, one on oxygen and one on air-filled canisters at the flow rate identified during the first session, in random order, with a rest of at least 20 minutes between tests. Oxygen flow rates to be provided to the patient will be determined during the screening visit on the basis of the 6MWT on O₂, as the flow needed to provide and to maintain optimal oxygen saturation ≥ 90% for at least half of the 6MWT duration, where possible, and/or a maximal flow of 10L/min (7).

The patient will be blind to the content of the canisters.

Patients will then be randomised as to the order in which they will receive the portable oxygen *versus* no oxygen for the first two weeks of the treatment period as outlined in Section 9.2.

The treatment period of the study will consist of a four week randomized crossover trial of ambulatory oxygen for use during physical activity. At Visit 2, eligible patients will be asked to:

- complete the K-BILD questionnaire(14) (see “primary outcome” section) and three other questionnaires (the Shortness of Breath Questionnaire (SOBQ) (15), St George’s Respiratory Questionnaire (SGRQ) (16), Hospital Anxiety and Depression Scale (HDAS) (18), see below section 10.5);
- Concomitant medication review;
- Adverse Event
- Pulse oximetry at rest on room air
- 6MWT one on oxygen at the optimal flow rate identified during the screening visit
- 6MWT on air

The two 6MWTs (one on oxygen the other on air cylinder) will be undertaken in random order, with a rest of at least 30 minutes between tests. The patient will be blind to the content of the canisters. 6MWT measured parameters will include 6-minute walk distance, oxygen saturation and heart rate measured continuously (WristOx2™ model 3150), Borg dyspnoea and Borg fatigue score before and at the end of the test, time to recovery of heart rate, oxygen saturation, Borg dyspnoea and Borg fatigue.

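### Section 17.5 rejects varying block sizes because the trial is un-blinded; open allocation is the reason to vary them, although the crossover design keeps the risk minor to moderate

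*Protocol*

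**What the plan says.** Section 17.5 gives the method in two sentences. The first is "Simple block method randomization will be performed to determine the order of treatment". The second rules out a safeguard and gives its reason: "As the study is un-blinded, varying block sizes will not be required". No block size is stated.

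Section 9.2 covers two randomisations at the baseline visit. The one at issue is "Randomisation as to the order in which subjects will have the portable home oxygen" or none in the first two weeks. On delivery, it says that the Trust statistician "will provide a master randomization list that will form basis of the study randomization", run through the InForm database. Neither section says whether the list is stratified by site, or whether the block size is kept from sites.

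Three other statements set the context:
- Home treatment is open. Section 6.1: "All this aside, blinding is legally impossible".
- Order is allocated at Visit 2, where, under section 10.4, "stability of respiratory symptoms will be assessed according to routine clinical care".
- On recruitment, section 17.3.2 says "we are confident of recruiting 50 patients at RBH, and 15 each at KCH and Aintree over this period".

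**The concern.** Varying block sizes exist to stop someone who can see past allocations from deducing the next one. If past allocations were masked, a fixed block would give little away. Here they are known to staff and patient alike, so the feature that section 17.5 cites for dropping the safeguard is the one that creates the need for it. The sentence also tells every reader that the block size is constant, so a site could infer it from its own run of allocations. Central allocation through InForm stops staff from reading ahead in the list; it does not stop deduction.

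There is motive and some opportunity to act on such knowledge. Section 4.6 says that physicians at the three centres would offer these patients ambulatory oxygen anyway, and section 4.5 accepts that the weeks without it may bring more breathlessness and fatigue. Eligibility is confirmed at the visit where order is assigned, and section 10.1 lets visits move by 7 days either way. At stake is whether the two sequence groups are comparable in how their patients would change over the four weeks.

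**Working it through.** **Inputs.** Planned total 80, split 50/15/15 (section 17.3.2); difference 8, SD 20, 90% power, 5% significance, 15% dropout (section 17.3.1). Block sizes of 2, 4 and 6 are assumptions.

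**The plan's own figure.** Section 17.5 states none; the only figure used here is the total of 80. It reproduces if 20 is read as the SD of the paired difference. The normal approximation gives (20 × (1.96 + 1.2816) / 8)² = 65.7, so 66; the exact paired t calculation gives 68; and 68 / 0.85 = 80. Nothing below changes it.

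**Upper bound on certain predictions.** The observer knows the block size b and sees every earlier allocation in the block. The next order is certain once one sequence has used its b/2 places.
- b = 2: the second place is always certain, so 1 of 2 = 50% (40 of 80).
- b = 4: up to relabelling, the blocks are AABB, ABAB and ABBA, with 2, 1 and 1 certain places. The mean is 4/3, and (4/3)/4 = 33% (about 27 of 80).
- b = 6: enumeration of all 20 blocks gives a mean of 1.5, and 1.5/6 = 25% (20 of 80).

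All three equal 1/(b/2 + 1).

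**One list interleaved across sites.** Suppose staff see only their own site's patients, who fill each list place with probability p, and (generously) know each patient's place in the block. Enumeration gives a certain share of p^(b/2) / (b/2 + 1).

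| Site | p | b = 2 | b = 4 | b = 6 |
|---|---|---|---|---|
| 50 patients | 50/80 = 0.625 | 31% | 13% | 6% |
| 15 patients | 15/80 = 0.1875 | 9% | 1% | 0.2% |

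Without knowledge of list places, simply guessing against the site's own running imbalance was right about 51 to 55% of the time in simulation (blocks of 4 and 6).

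**What varying sizes achieve.** Simulated for an observer who sees every allocation and knows the set of sizes but not the draw:

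| Scheme | Certain | Best guess correct |
|---|---|---|
| Fixed 4 | 33% | 70.8% |
| Fixed 6 | 25% | 68.3% |
| Varying 4/6 | about 5.5% | about 69% |
| Varying 2/4/6 | about 4% | about 70% |

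Most certain predictions go; most of the guessing advantage stays.

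**How this reaches the estimate.** Let τ be the true effect of oxygen, and let D₁ and D₂ be the mean changes from period 1 to period 2, apart from treatment, in the oxygen-first and oxygen-second sequences. The within-patient difference (oxygen minus none) averages τ − D₁ in the first and τ + D₂ in the second. With equal sequence sizes the paired mean is

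τ + (D₂ − D₁)/2.

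- *Stable level:* appears in neither D, so it cancels. A simulated 5-point level difference between sequences left the estimate at about 8.
- *Common period effect π* (D₁ = D₂ = π): cancels when sequences are balanced. With unequal numbers the bias is π(n₂ − n₁)/(n₁ + n₂); for a 36/32 split of 68 completers its size is 4/68, about 6% of π.
- *Selection on expected change* (D₁ ≠ D₂): bias is half the difference. As an illustration only, differences of 1 to 4 K-BILD points would give 0.5 to 2 points against the planned 8. A period term does not remove this, because it assumes the same period change in both sequences.
- *Differential dropout:* can make D₁ and D₂ differ among completers even if they were equal at entry.

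**The case against.** The strongest reply is that little harm can follow. Only the order is predicted, every patient receives both conditions, and the planned comparison is within patient. This stands, and it limits the severity. A reader might infer that holding back a breathless patient who is due to start without oxygen biases the result. If that patient is simply more breathless throughout, the selection is on level and cancels; it matters only if the patient is expected to change over the four weeks. A reader might also infer that period trends alone turn predictability into bias. With balanced sequences a common trend cancels, and blocking keeps the sequence counts close.

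The second reply is that 50/33/25% is a worst case. That also stands: these are upper bounds, only later places in a block are ever certain, and interleaving cuts the share sharply at the two smaller sites. The largest site still sees most of an interleaved list.

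Third, discretion at Visit 2 is narrow. Stability means no medication change and no chest infection in the preceding four weeks, and consent comes two weeks earlier. This stands in part: the check follows routine care and visit dates can move.

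Finally, block size and stratification are often specified outside the protocol. Silence on them is therefore no fault, and the text does not support saying that blocks are not formed within site. But section 17.5 is not silent on varying sizes: it dismisses them, for a reason that points the other way.

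**Conclusion.** The point holds as a minor to moderate weakness in allocation concealment. The reason in section 17.5 is inverted, and the safeguard that it sets aside suits an open trial. Under assumed fixed blocks of 2, 4 or 6, at most 50%, 33% or 25% of orders are certain in advance to someone who knows the size and sees all earlier allocations. With one interleaved list, the 50-patient site falls to about 31%, 13% or 6% even if staff know each patient's list place. The actual share cannot be fixed, because neither the block size nor the list structure is stated.

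It would be too strong to say that the next sequence is generally predictable, or that the treatment estimate is biased. The documents show a removable vulnerability. Bias would require selection on expected change over the four weeks, or differential dropout.

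**What to change.** Delete the second sentence of section 17.5 and state instead: *Treatment order is allocated through the InForm system by permuted blocks of randomly varying size; block sizes are held by the statistician and the database team and are not disclosed to sites.* The sizes themselves should stay out of the protocol.

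Stratification by centre is optional. It is a trade-off: it places whole blocks within one site, where staff see every earlier allocation, so with a fixed block it would raise predictability. If used, combine it only with varying, undisclosed sizes.

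The sample size does not change and the central system is already planned. The cost is regenerating the list and, if the change is deemed substantial, a protocol amendment with the approvals described in section 20. Adding stratification would also mean reconfiguring InForm. The gain is limited too: varying sizes remove most certain predictions, but little of a good guesser's advantage.
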